## Abstract

**BACKGROUND:** Work is a major social determinant of health. In people with serious mental illness (SMI), work is associated with better wellbeing, physical and mental health, quality of life, and may prevent the onset of disability. Among Veterans with SMI, work is a protective factor against suicide.

Most Veterans with SMI are unemployed and suffer substantially worse health and recovery across key domains. Despite quality VHA vocational services, such as supported employment (SE), two-thirds or more of Veterans who receive these services experience work dysfunction. A probable explanation lies in unsolved cognitive and behavioral barriers, such as low work-related self-efficacy, ineffective coping skills, little hope that work is attainable, poor work motivation and sense of self.

The Cognitive Behavioral Therapy for Work Success (CBTw) intervention was designed to target these problems and augment VHA SE services to synergistically improve work, as well as health and recovery, in Veterans with SMI. In an open trial pilot, CBTw was associated with significant increases in hours worked and wages earned and the majority of CBTw participants became steady workers. Veterans also experienced improvements in symptoms, recovery, and quality of life.

**PROJECT GOALS:** Using a randomized controlled trial (RCT) design over a 12-month study period at 3 VA SE programs, this project will 1) test the effects of CBTw on competitive work; 2) test the effects of CBTw on health and recovery outcomes; 3) Informed by the RE-AIM framework, conduct an implementation evaluation of CBTw to inform future wide scale roll-out of the intervention across the Veterans Health Administration (VHA).

### OBJECTIVES:

Aim 1: Test the effects of CBTw + SE compared to a control of psychoeducation + SE on work.

Hypotheses: Participants in the CBTw+ SE arm will work significantly more total weeks in competitive jobs (primary study outcome) and will be more likely to become steady workers.

Aim 2: Test the effects of CBTw + SE on health and recovery.

Hypotheses: Participants in the CBTw + SE arm will have greater improvements on subjective recovery and health-related quality of life, and decreases in symptoms, suicidal ideation, and inpatient service utilization.

Aim 3: Conduct an evaluation of the implementation of CBTw using VA supported employment staff to deliver the intervention. Implementation evaluation will examine the following RE-AIM domains: Reach—number of Veterans who take part and complete CBTw. Effectiveness—examined in Aims 1 and 2. Adoption—factors that influence uptake by SE programs examined via interviews and during site visits. Implementation—fidelity to CBT model (collected during monthly assessments)-primary Aim 3 outcome; and key barriers and facilitators to CBTw implementation gauged via site visits and key informant staff interviews. Maintenance—factors that influence continued CBTw use across time examined through key informant staff interviews.

### METHODS:

WORKWELL is a pragmatic, Hybrid 1 design RCT. CBTw will be tested at 3 SE sites—Roudebush VA Medical Center, the Edward J. Hines VA Medical Center, and the VA St. Louis Health Care System. 276 unemployed Veterans with SMI will be randomly assigned to receive CBTw plus regular supported employment services or a control of psychoeducation plus regular

supported employment services. Outcomes including total weeks worked in competitive jobs (primary study outcome), achievement of steady work, symptoms, recovery, health related quality of life, suicidal ideation, and service utilization will be assessed at posttreatment (12 weeks), 6 months (primary endpoint), and 9 months (to examine sustained effects). Competitive work outcomes will also be assessed at 12 months. Aim 1 and Aim 2 work and recovery outcomes will be analyzed using multilevel modeling to compare the intervention and control groups over time. CBTw implementation planning, training, and consultation will be provided to SE staff persons delivering the intervention. CBTw implementation outcomes will be analyzed using a rapid mixed methods approach.

## List of Abbreviations

BDI-II: Beck Depression Inventory-II

CAPRI: Compensation and Pension Record Interchange

CBT: Cognitive Behavioral Therapy

CBTw: Cognitive Behavioral Therapy for Work Success Intervention

COFAM: [name] and [name] completed HSR&D IIR study, "Comparison of Fidelity Assessment Methods"

CDA: Career Development Award

CDW: Corporate Data Warehouse

CFIR: Consolidated Framework for Implementation Research

CPRS: Computerized Patient Record System

CTS-R: Cognitive Therapy Scale-Revised

CWT: Compensated Work Therapy

DSM-5: Diagnostic and Statistical Manual of Mental Disorders, Fifth Edition

ERIC: Expert Recommendations for Implementing Change (resulted in a compilation of implementation strategies)

Hines: Edward Hines Jr. Hospital (study site)

HSR&D: Health Services Research and Development

ICC: Intraclass Correlation Coefficient

IMR: Illness Management and Recovery

IVIP: Indianapolis Vocational Intervention Program

MAR: Missing at Random

MCAR: Missing Completely at Random

MCS: SF-12 Mental Component Summary

NIMH: National Institute of Mental Health

PCS: SF-12 Physical Component Summary

PRISM: Expansion of RE-AIM implementation framework including inner and outer settings factors

PTSD: Post traumatic stress disorder

QUERI: Quality Enhancement Research Initiative

RA: Research Assistant

RAIN-MH: [name] HSR&D funded study, "Evaluation of Recovery-oriented Acute INpatient Mental Healthcare"

RCT: Randomized Controlled Trial

RE-AIM: Implementation science framework intended to translate research findings into practice; includes domains of Reach, Effectiveness, Adoption, Implementation, Maintenance

RLR: Richard L. Roudebush VA Medical Center

St. Louis: St. Louis VA Health System (study site)

SE: Supported Employment

SF-12: 12-Item Short Form Health Survey

SMI: Serious Mental Illness

SWS: Satisfaction with Services Scale

TSES: Therapeutic and Supported Employment Services, VA Central Office

VA: Veterans Administration

VACO: Veterans Affairs Central Office

VHA: Veterans Health Administration

VISN: Veteran Integrated Service Networks

VistA: Veterans Health Information System and Technology Architecture

VRC: Vocational Rehabilitation Counselors

WORKWELL: [name] proposed HSR&D study, "Work as a determinant of health: A pragmatic trial of enhanced cognitive behavioral therapy to bolster competitive work and wellness in veterans with serious mental illness"

## 2.0 Introduction

Among Veterans with serious mental illness (SMI), employment problems are pervasive. Over 1 million Veterans have a serious mental illness (SMI), formally defined by SAMHSA and the VA as the presence of a mental disorder that substantially limits role functioning, including work, and encompasses diagnoses of major depression, bipolar disorder, posttraumatic stress disorder (PTSD), and schizophrenia-spectrum disorders. Compared to unemployment of around 4.5% in the general Veteran population, over 75% of Veterans with SMI are unemployed. In studies across groups, such as female Veterans, Veterans of Post-911 conflicts, and other combat eras, SMI is linked with worse work outcomes. This problem is especially troubling because most people with SMI desire to work; many search for a job with little success. Even among the tens of thousands of Veterans with SMI who receive VHA employment services yearly, which focus on helping Veterans obtain community jobs, two-thirds or more continue to experience work deficits.

Employment problems in Veterans with SMI are costly at the personal and societal level. Unemployment in Veterans with SMI is associated with a higher risk of poverty and greater reliance on entitlements and the service system^10. Veterans with SMI report greater financial troubles, more difficulties covering basic needs, and higher debt. Overall, unemployment creates a deleterious feedback loop of poverty, declining mental status, and related problems, such as substance misuse. Similarly, studies have highlighted that among Veterans with SMI, the problem of lack of participation in the workforce has major economic and well-being effects that persist into the future, if not adequately addressed.

Supported by public health research, employment is a major social determinant of health. Employment dysfunction leads to poor health and wellness, including among those with SMI receiving quality employment services. In the general population, precarious employment has many chronic physical health effects and is a major cause of distress and poor mental health. Because people with SMI are particularly susceptible to the negative outcomes linked with unemployment, the effects are more damaging and include poor recovery, worsening illness trajectory, and more days of psychiatric hospitalization. In addition, Veterans with SMI have more medical conditions and experience deteriorating quality of life. These health problems also persist in unemployed persons with SMI who receive quality employment services.

Sustained work is associated with improvements in health and recovery in SMI, a Health Services Research and Development (HSR&D) priority. Across prospective studies, the health and wellness benefits of work in people with SMI who are receiving employment support include improved self-esteem and life satisfaction, a reduction in psychiatric symptoms, and fewer hospitalizations. In addition, studies of Veterans with SMI and broader meta-analysis evidence

indicates that work leads to major gains across health, quality of life, and wellness areas. These health and recovery benefits are particularly strong when persons engage in steady, long-term competitive work. Competitive work refers to a regular community job open to anyone, and pays at least minimum wage.

Competitive employment also leads to lower healthcare utilization and lower service system costs. A study by Bush and colleagues found that people with SMI who had received employment services and worked in competitive employment over 10 years had significantly reduced service utilization and mental health costs compared with persons who worked little or inconsistently. Similarly, young adults with SMI who work use fewer mental health services, take fewer medications, and are less reliant on disability entitlements. Among this group, there is evidence that employment may delay or altogether prevent subsequent disability.

Aligning with a current major VA and HSR&D priority, employment is a protective factor against suicide, whereas unemployment leads to increased suicide risk. Meta-analytic evidence demonstrates that unemployment is associated with a significantly higher risk of suicide, a relationship that is particularly strong among people with mental illness. A large study found that Veterans with recent suicidal ideation were more likely to have PTSD and report psychosocial barriers, including work problems. On the other hand, a sense of purpose, such as that found through career, was negatively associated with suicidal thoughts. Similarly in a sample of Veterans with depression, compared to their employed counterparts; unemployed persons were more likely to have thoughts of self-harm^27.

Despite quality VHA employment services, employment dysfunction & poor wellness persist. To address work problems in Veterans with SMI, supported employment (SE) services have been widely implemented through VHA Therapeutic and Supported Employment Services (TSES), including 200 SE programs nationwide. VHA SE services are individualized and include a vocational assessment, rapid job search and placement in community jobs, collaboration with employers, and ongoing follow-along support after the job has been secured. Supported by robust evidence, high quality SE services assist Veterans with SMI to find and keep competitive jobs in the community. However, SE programs have achieved only partial success in improving outcomes, as 67% or more of Veterans with SMI receiving SE remain unemployed. A further challenge is retention, as those with SMI who obtain jobs struggle to maintain employment long-term, even in the context of quality SE support. Moreover, among many with SMI receiving SE services, these ongoing struggles to secure competitive work are linked with worse health and well-being outcomes across studiese.g., 17.

SE services are not designed to address complex cognitive and behavioral work-related barriers. SE services effectively address common barriers such as skills deficits, resume building deficiencies, employer-related factors, legal involvement, navigation of job accommodations, and job search needs. However, as demonstrated by an extant of literature and our prior work; these services incompletely address many key cognitive and behavioral factors that impact work success. Specifically in people with SMI, including those receiving SE, many cognitive and behavioral factors have been identified as work barriers or linked with poor work outcomes: low work-related self-efficacy and self-esteem^35, poor motivation, loss of hope that work is attainable, interpersonal problems, difficulties enacting coping on the job, and stress. Further, job tenure has been associated with one's perception of competence and efficacy on the job. In this regard, work may present a threat to one's sense of self, resulting in lowered belief in one's ability to maintain a job.

In response, cognitive behavioral therapy (CBT) approaches have been suggested to augment SE services and address cognitive and behavioral barriers to competitive work success. A vast majority of CBT interventions do not focus on functioning as a primary target.

CBT is an empirically validated, recovery intervention recognized as a best practice in SMI care. CBT is a standard component of VHA mental health services in treating anxiety, depression, bipolar disorder, PTSD, and schizophrenia. However, though traditional CBT interventions effectively treat psychiatric symptoms, findings regarding the impact of CBT on functioning have been mixed and effect sizes are small. One potential explanation for the lack of findings is that while CBT aims to restructure thoughts about symptoms and increase symptom coping; it does not directly address role functioning and hence may have less effectiveness in these areas. To address this gap, CBT interventions have begun to arise that emphasize correcting unhelpful cognitions and tailoring behavioral strategies directly pertinent to deficits in functioning.

Previous interventions combining CBT with rehabilitation practices have had positive results on role functioning in Veterans with SMI. A cognitive intervention focused on protected, time-limited noncompetitive work experiences had positive effects on work performance in people with chronic schizophrenia. Further, CBT combined with social skills training has shown benefits beyond the effects of CBT or social skills training alone, improving skills mastery and interpersonal functioning in Veterans with SMI.

CBT approaches also improve health and wellness in Veterans. Cognitive behavioral interventions, either alone or in combination with other approaches, have been shown to improve physical health, mental health, quality of life, and related indicators of health in Veterans and non-Veterans with SMI. In addition, CBT approaches have shown benefits to improve physical health and functioning in Veterans with other chronic conditions, such as musculoskeletal pain.

Moreover, CBT directly builds upon existing VHA SE services. Featuring the provision of concrete individualized services to assist Veterans in acquiring strong fitting jobs, SE involves job assessment, resume support, rapid job development, collaboration with employers, and follow along support. However, many Veterans with SMI in SE continue to falter in their work pursuits, due in part to unsolved personal issues, such as cognitive and behavioral obstacles. The use of an empirically supported, tailored CBT approach tackles these barriers and builds upon SE by providing interventions that SE is not designed or intended to provide. CBT is also a strong fit with the structure and goals of SE, as demonstrated in past studies and in SE stakeholder accounts.

In summary, an enhanced CBT approach optimized to promote community work and wellness has great potential to increase meaningful functioning, improve health and recovery, and mitigate risk for negative outcomes, such as suicide, in Veterans with SMI receiving SE services.

### **3.0 Objectives**

#### **3.1. Study Purpose.**

In partnership with the VA Office of Therapeutic and Supported Employment Services, the project is a pragmatic Hybrid 1 randomized controlled trial testing employment and recovery outcomes and examining implementation of CBTw at three VA SE programs in three VISNs—Richard L. Roudebush VA Medical Center, Edward Hines Jr. VA Hospital, and VA St. Louis Health Care System.

### 3.2. Specific Aims & Hypotheses.

Aim 1. Test the effects of CBTw + SE compared to a time and format matched active control of psychoeducation + SE on competitive work outcomes across the 9 month study period. A total of 276 unemployed Veterans with SMI will be randomized to CBTw + SE or the control arm of psychoeducation + SE. Assessed at posttreatment (12 weeks), 6 months (primary endpoint), 9 months and 12 months (to examine sustained effects), the primary outcome will be total weeks worked in competitive jobs. A secondary work outcome, achievement of steady competitive work (i.e. working at least 50% of the follow-up), will be compared between study arms across the 12 month follow up.

Hypothesis 1: Compared to the control arm, participants in the CBTw + SE arm will work significantly more weeks and will be more likely to become steady workers.

Aim 2. Test the effects of CBTw + SE compared to the control arm of psychoeducation + SE on health and recovery at posttreatment (12 weeks), 6 month and 9 month follow up periods. The study will determine the effectiveness of CBTw to improve key health and recovery outcomes including health-related quality of life, suicidal ideation, subjective recovery, symptoms, and mental health service utilization.

Hypothesis 2a: Compared to controls, participants in the CBTw + SE arm will have greater improvement on subjective recovery and health-related quality of life, and decreases in mental health symptoms, suicidal ideation, and inpatient service utilization.

Hypothesis 2b: Greater participation in competitive work will predict improvements in these outcomes over time.

Aim 3. Guided by the RE-AIM implementation framework, conduct an implementation evaluation of CBTw to inform future wide scale roll-out of the intervention across the VHA. Existing Vocational Rehabilitation Counselors (VRCs) at the 3 VA SE programs will deliver CBTw, supported by an initial implementation strategy bundle—site tailored implementation planning, CBTw training, and weekly consultation including audit and feedback. Informed by the RE-AIM implementation framework, data will be collected and utilized to tailor implementation during the study, with assessment of the following RE-AIM domains:

(1) Reach—number of Veterans who take part and complete CBTw. (2) Effectiveness—examined in Aims 1 and 2. (3) Adoption—factors that influence uptake by SE programs examined via interviews and during site visits. (4) a. Implementation—fidelity to CBT model (collected during monthly assessments), the primary Aim 3 outcome; and b. key barriers and facilitators to CBTw implementation gauged via site visits and interviews. (5) Maintenance—factors that influence continued CBTw use across time examined through staff interviews.

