## 5.6 Study Evaluations

### Data Collection Protocol for Study Aims 1 & 2

Conducted by onsite research assistants (RAs) blinded to arm assignment, outcomes assessments will take place at four time points: baseline, 12-weeks (posttreatment), 6 months, and 9 months. In addition, work outcomes will be collected monthly on Work Update Forms to lessen the burden of Veteran recall. This schedule will elucidate the trajectory of treatment effects over time, including early response and more sustained impacts on outcomes. Participants will receive \$20 for each completed outcome assessment (baseline, 12-week, 6 & 9 month only). After obtaining informed consent, the onsite RA will administer a baseline assessment to gather assessment data. Each assessment will take approximately 60 minutes. All baseline assessments will take place in person; 12 week, 6 month, and 9 month assessments may be done in person (first consideration) or by phone.

The primary work outcome, total weeks worked in competitive jobs, will be collected monthly and analyzed at all assessment points with the primary endpoint being 6 months to allow adequate time for CBT skills to be practiced and solidified. The 12 month endpoint will examine whether there are sustained effects of CBTw and determine whether there are differences between the arms on achievement of steady competitive work (Aim 1). Health and recovery outcomes will be examined between the arms at all assessment points to understand the impact of CBTw; the relationship between weeks worked and these outcomes will also be examined at all assessment points (Aim 2). Work outcomes may be collected in person or by phone.

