#### *Health and Recovery Outcomes (Hypotheses 2a & 2b)*

To test **Hypothesis 2a**, three-level linear regression models (i.e. mixed models) accounting for the nested nature of the data will be used to test the effects of CBTw + SE services compared to psychoeducation + SE on each of the continuous outcomes including recovery (RAS), health-related quality of life (PCS & MCS), symptoms (CCSM), and suicidality (SSI) over time. For the count outcome of service utilization, three level Poisson regressions will be used to examine group differences over time on number of days of inpatient hospitalization. If there is a problem of excess of zeros for utilization (e.g., no hospitalizations), hurdle negative binomial models will be used.

To test **Hypothesis 2b**, three-level linear regression models will examine the effects of work on health and recovery outcomes over time, with predictors of competitive weeks worked, time, weeks by time interaction, site membership and potential interaction between site and key predictors, potential covariates (i.e. controlling for baseline levels of health and recovery), as well as random effects to accommodate the potential non-independence due to repeated measures and group cohort effects.

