To test **Hypothesis 2b**, two-level linear regression models will examine the effects of work on health and recovery outcomes over time, with predictors of competitive weeks worked, time, weeks by time interaction, site membership and potential interaction between site and key predictors, potential covariates (i.e. controlling for baseline levels of health and recovery), as well as random effects to accommodate the potential non-independence due to repeated measures and group cohort effects.

Missing data: Aims 1 & 2

Missing data from Aims 1 and 2 will come in two different forms: missing by attrition and intermittent missing of observation. Using logistic regression, the effects of missing observations due to sample attrition will be examined by investigating the participant characteristics associated with dropout. If results reveal that data are missing completely at random (MCAR) or due to observed factors (MAR), the data will be analyzed using full information maximum likelihood, taking into account potential predictors for missingness. However, if the pattern of missing data is nonignorable, pattern-mixture models that includes variables defined by the participant's pattern of missing data will be used. Sensitivity analyses also will be performed to examine how the result will change based on different assumptions about the missing data, such as the missing work period having no work, the mean amount of work as available data from earlier follow-up periods, or full employment.

Account for Heterogeneity in the Sample

The study is limited to working aged Veterans with SMI who are unemployed at baseline, decreasing the heterogeneity of the sample. In addition, analyses will examine whether treatment effect will change as a function of the site membership and major characteristics of the study participants, such as different types of SMI diagnoses, age, and current substance use (e.g., users vs. non-users).

AIM 3 CBTw IMPLEMENTATION: OVERVIEW

The initial CBTw implementation strategy was informed by implementation science and developed based on our experience in the two CBTw pilots, stakeholder surveys and interviews, and feedback from operational partners. *In order to ensure successful implementation of CBTw during WORKWELL and wide-scale uptake following its completion, an evaluation of this initial implementation strategy and barriers and facilitators of implementation will be conducted, guided by the RE-AIM framework.*

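### Hypothesis 2b's model of work and health sets no window, lag or deciding term and adjusts at most for baseline health, so health-driven changes in work can appear as a benefit of work

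*Protocol*

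**What the plan says.** Protocol 3.2 states Hypothesis 2b as "Greater participation in competitive work will predict improvements in these outcomes over time". The outcomes meant are those of Hypothesis 2a, which end with "decreases in mental health symptoms, suicidal ideation, and inpatient service utilization".

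On timing, protocol 5.6 (Study Evaluations) says only that "the relationship between weeks worked and these outcomes will also be examined at all assessment points".

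On the model, the protocol's Data Analysis section (Hypotheses 2a & 2b) says that "three-level linear regression models will examine the effects of work on health and recovery outcomes over time". The SAP's Hypothesis 2b paragraph has a two-level model in its place, "with predictors of competitive weeks worked, time, weeks by time interaction". The protocol names the same predictors, and each document also includes site and its possible interactions. Both documents list potential covariates, glossed in the SAP as "controlling for baseline levels of health and recovery".

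Neither document says whether weeks are cumulative or counted since the last visit, whether they are lagged, or which of the weeks and weeks-by-time terms decides the hypothesis. Study arm is not among the 2b predictors.

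**The concern.** The model is worded as an effect of work, but the same association arises if health drives work. A Veteran whose symptoms lift after baseline is more likely to find and keep a job. That Veteran then has both more weeks worked and a better score at the next visit. The protocol's own introduction expects this direction: it defines serious mental illness by its limits on role functioning, including work, and lists low self-efficacy, lost hope and poor coping as barriers to work.

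Leaving out arm adds a second route. CBTw is meant to improve both work and health, so arm can be a common cause of the two.

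Hypothesis 2b is the only hypothesis that links work itself to health, which is the claim in the study title. As specified, it could support that claim when work has no effect.

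**Working it through.** The documents state no power or effect size for 2b, so there is no planned figure to reproduce. The check is a simulation in which the true effect of work on health is zero.

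**Inputs from the documents.** 276 Veterans, or 276 × 0.87 ≈ 240 after 13% attrition; follow-up scores at 12 weeks, 6 and 9 months; nobody competitively employed at baseline; type I error 0.05 (SAP, Aim 1 power; sidedness not stated). Taken as two-sided, this gives 2.5% in the direction of benefit.

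**Assumptions, not in the documents.** Health H = person intercept (SD 0.7) + monthly autoregressive deviation (SD 0.7, correlation 0.85), so SD(H) = √(0.49 + 0.49) ≈ 1. Measurement error has SD 0.4. Job changes follow last month's health:

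- logit P(start) = α + b·H
- logit P(loss) = λ − b·H

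with b = 0.3, 0.5 or 0.8, that is, odds ratios e^0.3 = 1.35, e^0.5 = 1.65 and e^0.8 = 2.23 per SD. Linear models with person-clustered standard errors stand in for the mixed model.

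**Results.** The false-benefit columns have no true effect of work. The detection columns have a true benefit present only while employed, and no health-to-work effect.

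| Model | False benefit at b = 0.3 / 0.5 / 0.8 | Detects 0.3 SD | Detects 0.5 SD |
|---|---|---|---|
| Main effect of weeks, baseline-adjusted | 12% / 29% / 58% (3% at b = 0) | 55% | 92% |
| Weeks since previous visit, adjusted for score at start of interval | 8% / 16% / 33% | 57% | 92% |
| Earlier-interval weeks, adjusted for score at end of that interval | 7–9% | 2.5% | 4% |

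Against 2.5%, the first row is inflated 12/2.5 = 4.8-fold to 58/2.5 = 23-fold, and the second 8/2.5 = 3.2-fold to 33/2.5 = 13-fold.

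**Window.** A separate simulation (240 completers, weekly job changes, 13-week autocorrelation 0.8, reliability 0.8, two-sided 5% tests, log odds ratio 0.2 / 0.4 / 0.6 / 0.8 per SD) kept only baseline adjustment. Cumulative weeks were falsely significant in 16% / 42% / 73% / 92% of trials, and weeks since the last visit in 21% / 59% / 90% / 98.5%. At zero the rates were 5.5% and 4.2%. Shortening the window alone therefore makes matters worse; the start-of-interval score does the work.

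**Deciding term.** Under the first health process, the weeks-by-time interaction (linear time) gave false benefit in only 1.5%, 0.4% and 0.2% of trials and the opposite sign in 6.5%, 10% and 24%. With the interaction in the model, the weeks effect evaluated at 6 months was falsely positive in 13%, 26% and 62%. The answer depends on a choice the plan leaves open.

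**Which visits the second row covers.** At 12 weeks the previous score is the baseline score, so the added adjustment does nothing there. A rerun (276 Veterans, 1,000 trials, α = −3.1, λ = −2.0, 33–37% ever employed) came close to the second row when only the 6- and 9-month visits were outcomes: 10%, 18% and 38%, with detection 55% and 92%. Pooling in the 12-week visit gave 12%, 26% and 59%.

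**Inpatient days.** If a hospital week only prevents work that week and ends the job, weeks worked were significantly linked to fewer hospital days over the same 39 weeks in 37%, 63% and 87% of trials, at assumed weekly admission probabilities of 0.5%, 1% and 2%.

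**The case against.** The case for leaving the plan alone has real content.

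- **Time order is not absent.** A reader might infer that nothing puts work before health. That goes too far: all Veterans lack a competitive job at baseline, weeks accrue before the visit's scales are completed, and baseline health may be adjusted for. This stands, but it does not deal with health changes between baseline and the visit.
- **The exposure is undefined.** A reader might assume a running total paired with the same visit. Neither document says so. The gap is an unstated window and lag, and both obvious choices fail in simulation.
- **The false benefit belongs to one coefficient.** The interaction does not show it. This stands, and is why the deciding term must be named.
- **A fully lagged model looks like the cure.** Regressing later health on earlier-interval work, given health at the end of that interval, lowers the false rate. But that score is taken after the work was done, so any benefit already gained is adjusted away: detection falls from 55% to 2.5% and from 92% to 4%. A benefit that accumulates with each month worked does survive the lag (96% against 99%), so the model has a use, but it answers a narrower question.
- **Inpatient days.** They enter 2b only through the wording of protocol 3.2. The SAP's Aim 2 models do not list them, so a reader should not take it that the SAP specifies such an analysis.
- **Importance.** 2b is missing from the abstract's hypotheses, and protocol 5.6 calls the link a relationship. This limits the weight of the point; the analysis sections still present it as what work does to health.

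**Conclusion.** The point holds in this form: as specified, 2b cannot separate work improving health from health enabling work, and the weeks main effect can show a benefit where none exists. The size is about 12% to 58% of trials against 2.5% nominal. It rests on an assumed strength of health-to-work dependence, an assumed health process and assumed job-turnover rates, with site and cohort effects left out. The direction agreed across simulations with different assumptions; the exact rates should not be read as estimates for this trial.

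Two stronger conclusions might be inferred and are not supported. The documents do not show that work fails to improve health, only that this model could not tell. Nor does the problem reach the randomised comparisons: Hypotheses 1 and 2a compare arms and are unaffected. The point should be corrected, but it does not threaten the primary analysis.

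**What to change.** In the SAP's Hypothesis 2b paragraph and the matching protocol paragraph in 5.6 Data Analysis:

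1. Use the monthly work data to define the exposure as competitive weeks worked since the previous visit.
2. Adjust for the outcome at that previous visit (the start of the work interval), its baseline value, arm and site.
3. Name the coefficient that decides the hypothesis. Base it on the 6- and 9-month outcomes and show 12 weeks separately, since the previous score there is the baseline score.
4. Report the result as an association, not an effect of work.
5. Keep the fully lagged model as a sensitivity analysis, not the replacement.
6. State whether inpatient days belong to 2b. If they do, do not read a same-window association with weeks worked as a benefit of work, because hospital days directly displace work.

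The cost is SAP and protocol wording and a little more analysis. The monthly work data and visit scores are already collected. In the simulated cases power was kept (57% and 92%, against 55% and 92%). The downside is that bias remains: false benefit of about 8% to 33% over the assumed range, which is why item 4 is needed even with the better model.
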